### **3.0 Research aims and objectives**

### 3.1 Research aims

To evaluate the symptom burden and underlying pathophysiology of Long COVID syndromes in non-hospitalised individuals and to co-produce a remotely delivered intervention for supporting individuals with Long COVID syndromes. Data will also be used to inform the development of a feasibility study to evaluate the intervention produced during this project, and to plan future evaluations of supportive and pharmacological interventions for Long COVID symptoms. This will be done under a separate, linked protocol.

### 3.2 Research Objectives

1. To establish a representative population-based cohort of non-hospitalised individuals with COVID-19 and prolonged symptoms ("Long COVID").
2. To develop and validate a new patient-reported outcome (PRO) measure of symptom burden in individuals with Long COVID.
3. To collect validated PROs including symptoms, quality of life and work capability data longitudinally from the representative cohort of individuals with Long COVID using the Aparito Atom5™ platform.
4. To identify distinct symptom clusters ("syndromes") in non-hospitalised individuals with Long COVID and compare these Long COVID syndromes to known post-viral syndromes.
5. To measure immunological, proteomic and miRNA biomarkers to determine the underlying pathogenesis associated with Long COVID syndromes. To measure physical parameters via a wearable device to determine the physical exertions (heart rate intensity and movement) and sleep patterns observed in Long COVID syndromes.
6. To make recommendations on pharmacological and supportive therapies that: i) should be implemented without need for further evaluation; ii) should be evaluated in a clinical trial, and iii) should not be recommended for treating long COVID based on the available evidence.
7. Co-produce a supportive, remotely delivered intervention for individuals with long COVID, to address the symptoms associated with each Long COVID syndrome.
8. To evaluate patient and public involvement in the study.

### 4.0 Research Outputs and Deliverables

[figure not shown]
1. To establish a population-based representative cohort of 4000 individuals (minimum 2000) with COVID-19, with a minimum of 500 individuals with Long COVID, 500 matched control patients without COVID-19 (control group 1) and 500 matched control patients with COVID-19 but without Long COVID (control group 2). We will capture detailed data on symptoms, quality of life, work capability and objective health measures for individuals with Long COVID and patients in the matched control groups. This will include the development and validation of a new disease-specific PRO of symptom severity and interference for individuals with Long COVID.
2. To develop a new, validated PRO for the measurement of symptom burden in individuals with Long COVID: the Symptom Burden Questionnaire™: Long COVID.

3. To describe distinct Long COVID syndromes and their epidemiology and characterise their immune, inflammatory and proteomic profile, and physical parameters (heart rate intensity, sleep and movement) providing mechanistic understanding of each syndrome and identifying potential therapeutic targets for future evaluation. This will accelerate the identification of potential therapies for Long COVID that are targeted to each syndrome. Based on symptom clusters we will identify up to 200 individuals from the Long COVID cohort, 50 matched control patients without COVID-19, and 50 matched control patients with COVID-19 but without Long COVID to receive bio-sampling and be provided with wearable devices (Garmin Vivosmart4) to measure heart rate, oxygen saturation, step count and sleep quality (BioWear Sub-Study). This will be used in WP2 to deep phenotype Long COVID syndromes.
4. To co-produce a targeted intervention for Long COVID syndromes that can be delivered remotely on a digital platform. This intervention will have patients and carers at the heart of its design and will be based on the best available evidence on Long COVID. It will be designed to be effective, targeted to address symptoms associated with each specific syndrome, acceptable to patients, and scalable.

We will fulfil these objectives through four work packages (WPs). Work package 4 will be undertaken following further ethical review and approval of a substantial amendment to this study. We will hold regular patient and public involvement and engagement (PPIE) meetings throughout the project to ensure that we obtain and incorporate input from patients and members of the public and will actively engage with members of the LongCovidSOS campaign.

**Figure 1: Overview of the TLC Study (including future planned work)**

## 5.0 Study design

### **WP1: Establish a representative population-based cohort of individuals with Long COVID and collect patient-reported outcomes (PROs) (Objectives 1, 2 and 3)**

#### **Overview**

We will establish a population-based representative cohort of individuals with COVID-19 and matched controls. We will capture detailed data on symptoms, quality of life, work capability and objective health measures for individuals with Long COVID. This will include the development and validation of a new disease-specific PRO measure that will be used to assess the symptom severity and interference for individuals with Long COVID.

#### **Establish a representative population-based cohort of individuals with Long COVID (Objective 1)**

A representative population-based cohort of non-hospitalised individuals with Long COVID will be established using primary care records in the Clinical Practice Research Datalink (CPRD) and recruitment through the Interventional Research Services Platform (IRSP). We will use linked data from the Second-Generation Surveillance PCR-confirmed COVID-19 registry to identify all confirmed COVID-19 patients in CPRD. Using linked Hospital Episode Statistics (HES) data we will identify and exclude hospitalised patients. Further details on each of the data sources is provided (Box 1).

All potential cases will be reported to the Clinical Practice Research Datalink's (CPRD) Interventional Research Services Platform (IRSP). This is a web-based research platform linked to CPRD's anonymised primary care database of coded clinical electronic health care data from approximately 1700 practices across the UK. The platform enables primary care staff to review pre-selected patient lists, confirm eligibility and invite patients to join a study. The selection criteria are applied within the CPRD IRSP, based on the predefined patient selection strategy. A delegated health professional at each practice can subsequently access the pseudonymised patient list, re-identify the patients, and review the clinical record to a set of screening questions. For patients that meet selection criteria, the primary care team will send out an invitation letter informing them about the study and containing key links and information required to enable enrolment onto the study.

Via IRSP, all potential cases will be presented to participating general practices to review their suitability for study recruitment. Those assessed as suitable for study recruitment will be sent an invitation letter to participate in the study. We aim to recruit a minimum of 2000 individuals with COVID-19. Individuals from underrepresented sociodemographic groups (e.g., Black and Minority Ethnic (BAME) and those from areas of high socioeconomic deprivation) will be oversampled. These individuals with COVID-19 (minimum n=2000) will be invited to report symptoms, quality of life and work capability through the Aparito Atom5™ digital platform. Data collected from this cohort of patients with COVID-19 will be used to identify a sub-cohort of patients with long-term symptoms of Long COVID (minimum n=500, aiming for n≥750).

Patients with COVID-19 will be propensity score matched to patients without a COVID-19 diagnosis (minimum n=500), who will similarly be invited to participate in the study following eligibility checking by their general practice. This will constitute control group 1. Propensity scores will be estimated for the likelihood of COVID-19 using logistic regression, including the following data obtained from CPRD Aurum: age, sex, socio-economic status, body mass index (BMI), smoking status, comorbidities and risk factors for COVID-19 identified by Public Health England. A second control group of at least 500 participants will be derived from those with COVID-19 who do not report long-term symptoms (i.e., do not have Long COVID).

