### **Second-Generation Surveillance System (SGSS)**

SGSS is the national laboratory reporting system used in England to capture routine laboratory data on infectious diseases and antimicrobial resistance. The SARS-CoV-2 testing started in UK laboratories on 24/02/2020, with the SGSS data reflecting testing (swab samples, PCR test method) offered to those in hospital and NHS key workers (i.e., Pillar 1). The linked SGSS data only contains positive tests results. The primary care data itself includes both positive and negative Pillar 2 PCR and other RNA detection COVID-19 test results and it is estimated that over 80% of all such tests undertaken in England are being matched to GP records.

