## 6.0. Participant selection and Eligibility

### 6.1 Population-based representative cohort of individuals with COVID-19 (minimum 2000 participants)

#### 6.1.1 Eligibility Criteria

Non-hospitalised individuals with a positive RT-PCR test for SARS-CoV-2 in SGSS data linked to CPRD Aurum. Those from that cohort reporting symptoms associated with COVID-19 at least 12 weeks from the diagnosis will be defined as having Long COVID.

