#### 6.1.3 Exclusion criteria

Individuals without a positive SARS CoV-2 RT-PCR test result in CPRD Aurum.

Individuals with a hospital admission within 28 days of a positive SARS CoV-2 RT-PCR result in CPRD AURUM.

Individuals aged under 18 years.

Individuals unable/unwilling to provide informed consent.

Individuals unable/unwilling to undertake the protocol activities.

Individuals deemed appropriate for exclusion by their GP (e.g., on a palliative care register).

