## **6.2 Matched controls - Group 1 (minimum of 500 participants)**

### **6.2.1 Eligibility Criteria**

Propensity score-matched individuals without a diagnosis of COVID-19 (suspected or confirmed) in CPRD Aurum and without a positive SARS CoV-2 RT-PCR result in linked SGSS data and without a record of hospital admission within 28 days of the index date will comprise Control Group 1. For propensity score matching we will use covariates such as sociodemographic characteristics, lifestyle and metabolic profile measures and presence of comorbidities, especially those identified as risk factors for COVID-19.

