**Figure 2.0 Participant recruitment**

### **6.5.2 Matched controls**

Sampling from the CPRD Aurum database, we will generate a propensity score matched control population of 500 individuals without a positive SARS CoV-2 RT-PCR result (Control Group 1) and 500 individuals with COVID-19 without Long COVID (Control Group 2), to assess the additional burden of Long COVID symptoms beyond what is observed in the infected population. Propensity scores will be generated using data on sociodemographic factors, lifestyle and metabolic profile measures and comorbidities. Matching will be done using the nearest-neighbour algorithm without replacement, considering callipers of width equal to 0.1. The index date for matching will be 1st January 2020. The CPRD Aurum ID for the matched control patients within Control Group 1 will be provided to the CPRD IRSP. CPRD will inform participating GP practices of these patients by providing the corresponding EMIS codes and will ask them to check their suitability for recruitment. The list of suitable patients will then be recorded on IRSP with the generation of a unique Global ID. Researchers at the University of Birmingham will not have access to Patient Identifiable Data until they have consented to participate on Atom5™. Participating GP's will invite eligible patients to take part via invitation letters, text message or email which will contain a copy of the PIS and a unique on-boarding code. Patients willing to take part will be instructed to use the on-boarding code to register on the Atom5™ platform.

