## 8.0 Study procedures

### 8.1 Population-based representative cohort of individuals with long COVID and matched controls

Eligible individuals who wish to participate will download the Aparito Atom5™ app or visit the website and register using their unique one-time use on-boarding code. They will then be asked to provide electronic consent on the app or website, which includes confirming that participants with a positive SARS CoV-2 RT-PCR result have not been hospitalised within 28 days of being diagnosed with COVID-19. Control participants will be asked if they have ever had COVID-19 to check eligibility for inclusion as a control subject. Once the consent form has been completed, participants will be asked to complete a brief demographic and clinical questionnaire. The questionnaire will ask for the following details: name, sex, date of birth, contact number, postal address, ethnic group, GP address, height, weight, smoking status, pregnancy status, SARS CoV-2 vaccination status, confinement (shielding) status, care home residence, occupation, occupational status (in work, furlough, etc.), and over-the-counter medications used to manage symptoms. Full details of these questions are provided in the appendix (Baseline data collection in Atom5™) and in Table 1.0.

Participants will then be invited to report the presence of established Long COVID symptoms and quality of life using validated tools at monthly intervals for a period of 12 months. At each time point, participants will be asked to confirm their willingness to continue to participate in the study. Those wishing to withdraw will be asked to complete a withdrawal form and advised that any data collected up to that point will need to be retained as it will have been used in aggregated data analyses.

As requested by our PPI group, we will ensure that people who are unable to use the app or website (due to no access to a smartphone or internet connection, patient preference, language, or other requirements) can participate through nurse interview-led appointments (telephone or video conference) with translators as required. Information and contact numbers will be provided on the PIS. Alternative language versions of each PRO will be provided where validated translations exist (see table below) The translated questionnaires are currently being programmed on the app.

	English	Bengali	Polish	Welsh	Punjabi	Gujarati	Urdu
EQ5D5L	X	X	X	X	X	X	X
FACIT F	X	X	X		X	X	X
PHQ-2	X	X	X		X	X	
GAD-2	X		X		X	X	X

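### Control Group 1 is matched on a list that does not name occupation, although the SGSS case source probably over-represents NHS key workers, so contrasts with uninfected controls may partly reflect health or care work

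*Protocol*

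**What the plan says.** **Case source.** Section 6.1.1 defines the cohort as "Non-hospitalised individuals with a positive RT-PCR test for SARS-CoV-2 in SGSS data linked to CPRD Aurum". Box 1 in section 5.0 says SGSS reflects tests "offered to those in hospital and NHS key workers", that is Pillar 1, and places Pillar 2 results in the primary care record. Section 6.1.3 then excludes "Individuals with a hospital admission within 28 days of a positive SARS CoV-2 RT-PCR result in CPRD AURUM".

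**Control source.** Under sections 6.2.1 to 6.2.3, Control Group 1 comes from CPRD Aurum adults with no suspected or confirmed COVID-19 code and no SGSS positive. No condition is set on having been tested or on occupation.

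**Matching.** The covariates are described three times:
- Section 5.0, WP1, Objective 1, the only itemised list, taken from CPRD Aurum data: "age, sex, socio-economic status, body mass index (BMI), smoking status, comorbidities and risk factors for COVID-19 identified by Public Health England".
- Section 6.2.1: "covariates such as sociodemographic characteristics, lifestyle and metabolic profile measures and presence of comorbidities, especially those identified as risk factors for COVID-19".
- Section 6.5.2: "Propensity scores will be generated using data on sociodemographic factors, lifestyle and metabolic profile measures and comorbidities".

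**Occupation.** The baseline questionnaire in section 8.1 asks for "occupation, occupational status (in work, furlough, etc" among other items, and Table 1.0 lists both at baseline. The protocol does not say that either is used in matching or in a comparison.

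**The concern.** The two groups enter by different routes. By the protocol's own description, a non-admitted person could appear in SGSS largely because of NHS work; an uninfected control needs only to be registered and to have no COVID-19 record. A propensity score for the likelihood of COVID-19 that leaves out a driver of being tested can balance every listed covariate and still leave the groups different on that driver. Socio-economic status does not separate an NHS worker from another employed person.

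At stake are the contrasts that the protocol states against uninfected or matched controls:
- the epidemiology, health service use and mortality of each syndrome (WP2, Objective 4, part A);
- immune markers (WP2, Objective 5, part A);
- SBQ-LC known-groups validity, and the ROC analysis that sets a cut-off for recognising Long COVID in the general population (section 10.2).

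If health or care work is itself related to these measures, part of any difference would be credited to Long COVID, or part of a true difference would be hidden.

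**Working it through.** The protocol gives no figure on this point, so there is none to reproduce. The check has two parts.

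**1. Setting the sections side by side.**
- Box 1 names two SGSS streams: people in hospital and NHS key workers.
- Section 6.1.3 removes those admitted within 28 days of the positive test. This takes out most of the first stream, though not people tested in hospital and never admitted.
- The key-worker stream therefore forms a larger share of what is left.
- Sections 6.2.1 to 6.2.3 apply no matching restriction to controls.
- None of the three covariate statements names occupation. The itemised list adds Public Health England risk factors, but section 6.2.1 links such risk factors to comorbidities.

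An imbalance in key-worker share is thus likely under the plan as written, and nothing stated removes it.

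**2. How large it could be (illustration only).** The key-worker shares and the effect of key-worker status are not in the documents and are assumed. The group size of 500 v 500 uses the protocol's minimum numbers. The 50 v 50 size is one syndrome against Control Group 1 in the bio-sampling sub-study (section 6.4.1).

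Bias in SD units = (share in cases − share in controls) × key-worker difference in SD.

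With no true effect of infection, SE = √(2/n), z = bias/SE, and the chance of a two-sided 5% rejection = Φ(z − 1.96) + Φ(−z − 1.96).

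For n = 500, SE = √(2/500) = 0.0632. For n = 50, SE = √(2/50) = 0.2.

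| Cases v controls | Key-worker difference | Bias | Rejection, 500 v 500 | Rejection, 50 v 50 |
|---|---|---|---|---|
| 30% v 5% | 0.1 SD | 0.25 × 0.1 = 0.025 | 6.8% | 5.2% |
| 30% v 5% | 0.2 SD | 0.25 × 0.2 = 0.05 | 12.4% | 5.7% |
| 50% v 5% | 0.2 SD | 0.45 × 0.2 = 0.09 | 29.6% | 7.4% |
| 50% v 5% | 0.3 SD | 0.45 × 0.3 = 0.135 | 56.9% | 10.4% |
| 80% v 5% | 0.3 SD | 0.75 × 0.3 = 0.225 | 94.5% | 20.3% |

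Worked row: 0.135/0.0632 = 2.13, and Φ(2.13 − 1.96) ≈ 0.57. If occupation type were balanced or fully adjusted for, the share difference would be 0 and the rejection rate would return to 5%.

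The table makes no allowance for the part of the imbalance that correlated matching covariates would remove.

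**The case against.** Several points can fairly be put against this.

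- **Covariate adjustment usually belongs in the SAP, which is not shown.** This stands for the adjustment model, and an SAP may already include one. The matching list, however, is fixed in this protocol and is applied before invitation, so it decides who is recruited.
- **The covariate wording is open.** Sociodemographic factors could include occupation, and socio-economic status would absorb some of the imbalance. This stands in part. A reader might infer that matching cannot remove the difference at all; the documents do not go that far. They show only that occupation is not named.
- **The case mix is uncertain.** Section 6.1.3 refers to positives in CPRD Aurum, section 6.4.1 and the recruitment text of section 6.5.1 also mention a COVID-19 diagnosis, and people tested in hospital but not admitted remain eligible. Pillar 2 or diagnosis-based cases would dilute the enrichment. This stands: the cases are likely to be enriched, but not shown to be mostly key workers.
- **The size is assumed.** This stands. A reader might take the 57% row as the expected false-positive rate, but it is one chosen point in a range that starts at 6.8%. A null of no effect is also artificial for symptom scores, because the Long COVID group is defined by its symptoms.
- **The direction is not shown.** This stands. People fit for front-line work might use services less, which would hide burden. It is tempting to conclude that Long COVID burden would be overstated, but nothing in the protocol supports that.
- **Not every outcome has a stated contrast with Control Group 1.** This stands. A reader might extend the point to PHQ-2, GAD-2, PCL-2, work capability, sleep and step count. The protocol states no specific Control Group 1 contrast for these, and the digital phenotyping text uses wearable data to describe the syndromes.
- **Control Group 2 offers a cleaner comparison.** This stands. It comes from the same SGSS source and largely shares any enrichment. It does not replace the contrasts with uninfected people.

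**Conclusion.** The concern holds in a limited form. As written, the case source is likely to favour NHS key workers, the uninfected control source is not, and no covariate statement names occupation. The stated contrasts between Long COVID and Control Group 1 may therefore partly reflect being a health or care worker.

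The size cannot be derived from the documents. Under the assumed values it runs from negligible (0.025 SD) to material (0.225 SD at 500 v 500), and the sign is unknown. The conclusion rests on taking Box 1's account of SGSS and the case definition in section 6.1.1 at face value, and it weakens to the extent that other test sources or coded diagnoses bring in cases. The point concerns the internal comparison with uninfected controls. It is worth acting on because the remedy is cheap, but confidence in its practical size is low.

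**What to change.** For the Long COVID v Control Group 1 contrasts, state that the analysis will:

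1. Code the baseline occupation item into health/care worker or not, and report its balance alongside the matching covariates.
2. Adjust for that occupation type. Do not adjust for current employment status, which Long COVID may itself have changed.
3. Repeat the main contrasts without health/care workers as a sensitivity analysis.

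The adjustment should not depend on work status before infection, because uninfected controls have no infection date and the items listed in section 8.1 and Table 1.0 are recorded at enrolment.

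The cost is a small amount of extra analysis, coding of the occupation item, and a check that its wording captures usual or pre-illness occupation. The full question text is in an appendix that is not shown, so a small change to the item may be needed. Recruitment and matching need not change.
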